8.3.4 Missing Safety-Follow up Period

Missing data in the Safety Follow-up Period will be handled in the same way as missing data in the DBTP.

8.4 Detection of Bias

This study has been designed to minimize potential bias by allocating treatment groups randomly, assessing endpoints and handling withdrawals without knowledge of the treatment. Other factors that may bias the results of the study include:

- important protocol deviations likely to impact the analysis and interpretation of the efficacy endpoints
- inadvertent breaking of the blind before formal unblinding
- investigational product dosing non-compliance
- the timing of and reasons for early withdrawal from treatment and from study

The incidence of these factors may be assessed. Important protocol deviations will be listed and/or tabulated in the CSR. If necessary, the incidence of other factors will be tabulated.

Any breaking of the blind for individual subjects prior to formal unblinding of the study will be documented in the CSR.

The timing of and reasons for early withdrawal from treatment and from study will be tabulated and/or listed.

8.5 Outliers

Histograms will be examined to identify outliers in any of the continuous variables used in the analyses. Unexpected and/or unexplained values in categorical data will be identified by utilizing frequency tables.

Outliers due to data entry errors will be corrected by the study team before final database lock. The validity of any questionable values or outliers will be confirmed. Outliers or any questionable values with confirmed validity will be included in the analyses. However, ad-hoc sensitivity analyses may be conducted to evaluate the influence of extreme values in the data.

8.6 Distributional Characteristics

Continuous endpoints of change from baseline value will be analyzed under normality assumption. If they deviate appreciably from normality, appropriate transformations or the non-parametric alternatives, may additionally be considered.

8.7 Validation of Statistical Analyses

Programs will be developed and maintained, and output will be verified in accordance with current risk-based quality control procedures.

Tables, figures, and listings will be produced with validated standard macro programs where standard macros can produce the specified outputs.

The production environment for statistical analyses consists of Amgen-supported versions of statistical analysis software; for example, the SAS System version 7.1 or later.

9. Statistical Methods of Analysis

9.1 General Considerations

The primary objective of this study is to evaluate the effect of AMG 301 compared to placebo on the change from the baseline period in monthly migraine days, in subjects with CM or EM.

The primary analysis will be performed when the last randomized subject completes the week 12 assessment or is discontinued from the study and all data are collected for the primary endpoint. The final analysis for the study including DBTP and safety follow-up phase will be performed at the end of the study.

Subjects will be analyzed based on their randomized treatment group assignment.

Summary statistics by each treatment group will be tabulated at each visit. For continuous endpoints, the descriptive statistics include: number of observations, means, medians, standard deviations, standard errors, first and third quartiles, minimums and maximums, and 2-sided 95% confidence intervals of the means (confidence intervals will be provided for efficacy endpoints only). For categorical endpoints, the summaries will contain the number and percentage of subjects in each category.

[figure not shown]
Change from baseline for efficacy endpoints during the DBTP will be summarized using the study baseline.

Primary analyses for efficacy endpoints are based on a linear mixed effects model including treatment group, baseline value, stratification factors, scheduled visit, and the interaction of treatment group with scheduled visit in the model.

Unadjusted p-values (not adjusted for multiple comparisons) will be provided for the comparisons between each AMG 301 treatment group vs. the placebo group for efficacy endpoints. For continuous efficacy endpoints, the adjusted mean change from baseline for each treatment group, and the adjusted treatment difference compared to placebo, associated 95% confidence intervals, and p-values for pairwise comparisons will be reported. For dichotomous efficacy endpoints, adjusted odds ratios compared to placebo, associated 95% confidence intervals, and p-values will be reported. Values for stratification factors as used during randomization will be utilized in the efficacy analysis instead of the subject's actual value. However, the actual value will be used in analyses of baseline characteristics or in the subgroup analyses of the efficacy endpoints.

To maintain a family-wise type I error rate at 0.10 for the primary endpoint, the AMG 301 210 mg treatment group and the AMG 301 420 mg treatment group will each be tested separately vs placebo at a significance level of 0.05.

CCI

9.2 Subject Accountability

The disposition of all randomized (enrolled) subjects will be tabulated by randomized treatment group. The summary for the DBTP will include the number of subjects who are randomized, the number and percent of subjects who receive/never receive the double-blind IP, who complete double-blind IP, discontinue double-blind IP and reasons for discontinuing, who complete the 12-week DBTP, and who withdraw prematurely from the study before completion of the 12-week DBTP and their reasons for withdrawal.

In addition, the number of subjects who complete the study or are continuing in the study and who withdraw prematurely from the study and their reasons for withdrawal will be summarized.

A footnote on the subject disposition tables will include the number of subjects screened.

A summary of the study reporting period including a description of key dates will also be provided, including dates of the first and last subject enrolled, the primary completion date (for the primary analysis) and the last subject's end of study date (for the final analysis).

9.3 Important Protocol Deviations

Important Protocol Deviations (IPDs) categories are defined by the study team before the first subject's initial visit and updated during the IPD reviews throughout the study prior to database lock. These definitions of IPD categories, subcategory codes, and descriptions will be used during the course of the study. Eligibility deviations are defined in the protocol.

All IPDs will be reported in the clinical study report.

9.4 Demographic and Baseline Characteristics

Subject demographic and baseline characteristics will be summarized using descriptive statistics by randomized treatment group and overall study population using FAS. If multiple races have been reported for a subject, the subject will be categorized as multiple races.

The following demographic and baseline characteristics will be summarized:

- Sex (categorical)
- Ethnicity (categorical)
- Race (categorical)
- **Age (continuous, categorical)**
- Region (categorical, North America vs. Rest of World)
- Height (continuous, cm)
- Weight (continuous, kg)
- Body Mass Index (continuous, BMI, kg/m²)
- **Baseline migraine type (categorical, CM vs. EM)**
- **Prior participation in CGRP trial (categorical)**
- **≥ 50% reduction in MMD after receiving erenumab for 3 months (Categorical)**
- **Targeted neurological disease diagnosis at baseline (categorical: migraine with aura, migraine without aura, depression, anxiety, other)**
- **Acute headache medication use during baseline phase:**
 - a) Migraine-specific
 - b) Non migraine-specific
- **Monthly acute migraine-specific medication days in subjects who received acute migraine-specific treatment (continuous)**
- **Monthly acute migraine-specific medication days (continuous)**
- **Number of prior migraine prophylactic treatment category failed (categorical)**
- **Beck Depression Inventory (BDI)-II total score severity grade (categorical)**
- **Age at onset of migraine (continuous)**
- **Disease duration of migraine with or without aura (continuous)**
- **Monthly migraine days (continuous)**
- **Monthly headache days (continuous)**
- **Modified Migraine-specific and Migraine Disability Assessment (MMIDAS) (continuous, categorical)**

- **Headache Impact Test-6 (HIT-6) (continuous, categorical)**
- **Migraine Physical Function Impact Diary (MPFID) (continuous)**
- **Cranial Autonomic Parasympathetic Symptom (CAPS) (continuous, categorical [0, \geq 1])**

9.5 Efficacy Analyses

Endpoint	Statistical Analysis Methods
Primary	
The primary endpoint, change in monthly migraine days from the baseline period to the last 4 weeks of the 12-week DBTP, will be analyzed using the generalized linear mixed effects model including treatment group, baseline value, stratification factors, scheduled visit, and the interaction of treatment group with scheduled visit using the PAS without any subject-level imputation for missing data. The primary endpoint will be tested for each AMG 301 treatment group (AMG 301 420 mg SC injections Q2W and AMG 301 210 mg SC injections Q4W) compared to the placebo group using appropriate contrasts for pairwise comparisons. Each AMG 301 dose will be compared to placebo at an alpha of 0.05 to maintain the family-wise type I error at 0.10. The mean change from the baseline period for each treatment group, and the treatment difference, 95% confidence intervals, and p-values will be reported.
 
Sensitivity analyses for the primary endpoint include an analysis of covariance model using data through week 12, in which missing values will be imputed using multiple imputation assuming MNAR up to week 12.

Secondary	
• At least a 50% reduction from the baseline period in monthly migraine days in the last 4 weeks of the 12-week double-blind treatment period: Comparison between treatment groups will be performed using CMH tests on observed data with stratification factors. The odds ratio for each AMG 301 treatment group versus placebo group, associated 95% confidence intervals, and unadjusted p-values will be reported. Sensitivity analyses for response include: a logistic regression model using data from week 9 through week 12, adjusting for baseline values where missing values will be imputed as non-responders.
• Change from the baseline period in monthly acute migraine-specific medication days in the last 4 weeks of the 12-week double-blind treatment period: The same analysis methods will be used as for the primary endpoint. Refer to Table 5 for details on other secondary endpoints.
CCI	

The primary analysis of efficacy endpoints will utilize the PAS. Subjects will be analyzed according to their randomized treatment group regardless of the actual treatment received during the study.

For primary analysis at week 12, the continuous change from baseline efficacy endpoints calculated by the method as specified in [Section 5.6](#) will be analyzed using generalized linear mixed effect models including treatment group, stratification factors, scheduled visit, the interaction between treatment group and scheduled visit and the baseline value on observed data. The dichotomous efficacy endpoints will be analyzed using the stratified Cochran-Mantel-Haenszel (CMH) test after the missing data are imputed as non-response. Detailed primary analysis methods, sensitivity analyses, and covariates included in the models are summarized in the table below.

Table 9-1. Summary of Efficacy Endpoints and Analysis Methods

Endpoint	Primary Summary and Analysis Method	Sensitivity Analysis
Primary Endpoint		
Change in monthly migraine days from baseline to the last 4 weeks of the 12-week DBTP (Note: Results from time points other than week 12 during the DBTP will also be generated in the same generalized linear mixed effect model.)	Analysis Method I: 1. Summary statistics by visit using observed data 2. Least squares means from a generalized linear mixed effect model including treatment group, baseline values, stratification variables, scheduled visit, and interaction of treatment and scheduled visit using observed data	1. Summary statistics by visit and analyze using an ANCOVA model with multiple imputation assuming MNAR(control-based pattern imputation) 2. Summary statistics by visit and analyze using an ANCOVA model with observed data 3. Subgroup analyses: Same as primary summary and analysis method.

Page 1 of 3

Footnotes defined on last page of the table

Table 9-1. Summary of Efficacy Endpoints and Analysis Methods

Endpoint	Primary Summary and Analysis Method	Sensitivity Analysis
Secondary Endpoints		
At least a 50% reduction from baseline in monthly migraine days in the last 4 weeks of the 12-week DBTP (Note: Results from time points during DBTP will also be generated in the same model.)	1. Summary statistics by visit using observed data 2. Stratified Cochran-Mantel-Haenszel (CMH) Test	1. Summary statistics by visit and analyze using a logistic regression model, and using responder rate calculated using monthly migraine days 2. A stratified Cochran-Mantel-Haenszel (CMH) test will be used after the missing data are imputed as non-response 3. A generalized linear mixed effects model will be used on observed data 4. Subgroup analyses: Same as primary summary and analysis method.
Change from baseline in monthly acute migraine-specific medication treatment days in the last 4 weeks of the DBTP (Note: Results from individual time point during the DBTP will also be generated in the same generalized linear mixed effect model.)	Analysis Method I (see above)	Analysis Method II: 1. Summary statistics by visit and analyze using an ANCOVA model with multiple imputation, assuming MNAR
Change from baseline in monthly physical impairment scores as measured by MPFID at assessment time points (Note: Results from individual time point during the DBTP will also be generated in the same generalized linear mixed effect model.)	Analysis Method I	N/A

Footnotes defined on last page of the table

Page 2 of 3

Table 9-1. Summary of Efficacy Endpoints and Analysis Methods

Endpoint	Primary Summary and Analysis Method	Sensitivity Analysis
Change from baseline in monthly impact on everyday activities scores as measured by MPFID at assessment time points (Note: Results from individual time point during the DBTP will also be generated in the same generalized linear mixed effect model.)	Analysis Method I	N/A
CCI	Analysis Method I	N/A
	
• Summary statistics by visit using observed data• Stratified CMH test	N/A

Page 3 of 3

^a The same analyses methods will be applied to the endpoints:

Change from baseline in headache impact scores as measured by HIT-6
Change from baseline in monthly average severity of migraine pain
Change from baseline in monthly acute headache medication treatment days.
Change from baseline in migraine-related disability and productivity as measured by MMIDAS
Change from baseline in monthly days with physical impairment as measured by the MPFID
Change from baseline in monthly days with impact on everyday activities as measured by the MPFID
Change from baseline in the monthly average overall impact on everyday activities score as measured by the MPFID
Change from baseline in the Cranial Autonomic Parasympathetic Symptom (CAPS) scale total score

^b The same analyses methods will be applied to the endpoints:

Response defined as a 100% reduction from baseline in mean monthly migraine days
Achievement of at least a 5-point reduction from baseline in mean monthly average physical impairment scores as measured by MPFID
Achievement of at least a 5-point reduction from baseline in monthly average impact on everyday activities scores as measured by MPFID

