4.1 Planned Covariates

Region (North America versus Rest of World) and baseline migraine frequency (CM versus EM) will be included in the repeated measures linear mixed models models as stratification factors. In addition, the baseline value corresponding to the endpoint being analyzed will also include.

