9.5.2 Analyses of Secondary Efficacy Endpoint(s)

For continuous secondary efficacy endpoints, summary statistics and primary analysis method will be conducted in the same way as that for the primary endpoints as specified in [Section 9.5.1](#).

For dichotomous secondary endpoints, comparison between treatment arms will be performed using a stratified CMH test for the primary analysis. Sensitivity analyses will use generalized linear mixed effects model on observed data, adjusting for baseline values and stratification factors with appropriate contrasts for pairwise comparisons. The odds ratio for each AMG 301 treatment group versus placebo group, associated 95% confidence intervals, and unadjusted p-values will be reported. Sensitivity analyses for response include: a logistic regression model using data through week 12, adjusting for baseline values where missing values will be imputed as non-responders.

Subgroup analyses are performed for secondary efficacy endpoints using the same method as primary analysis method but performed within each interested subgroup. The treatment difference (or odds ratio) with associated 95% confidence interval and p-values will be reported within each subgroup.

CCI

A large black rectangular box redacting content. The text 'CCI' is visible in the top-left corner of the redacted area.

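### The logistic non-responder sensitivity analysis of the 50% responder endpoint names baseline values but not region or CM/EM; adding the two randomisation factors is a small, free improvement

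*SAP*

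**What the plan says.** Randomisation is stratified by CM/EM and by region, North America against Rest of World (SAP 3.1; protocol 5.1). For response, defined as at least a 50% reduction in monthly migraine days over the last 4 weeks, the plan describes these analyses:

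- **Main analysis, SAP 9.5, secondary row:** "Comparison between treatment groups will be performed using CMH tests on observed data with stratification factors". SAP section 10 also says observed data.
- **Main analysis, SAP 9.5, text before Table 9-1:** "The dichotomous efficacy endpoints will be analyzed using the stratified Cochran-Mantel-Haenszel (CMH) test after the missing data are imputed as non-response".
- **Sensitivity, logistic, SAP 9.5:** "a logistic regression model using data from week 9 through week 12, adjusting for baseline values where missing values will be imputed as non-responders".
- **Sensitivity, logistic, SAP 9.5.2:** "a logistic regression model using data through week 12, adjusting for baseline values where missing values will be imputed as non-responders". Protocol 10.4.3.2 has the same wording. The logistic entry in Table 9-1 lists no covariates.
- **Sensitivity, CMH, Table 9-1:** "A stratified Cochran-Mantel-Haenszel (CMH) test will be used after the missing data are imputed as non-response".
- **Sensitivity, mixed model, SAP 9.5.2:** "Sensitivity analyses will use generalized linear mixed effects model on observed data, adjusting for baseline values and stratification factors".

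Two general rules bear on the covariates. In SAP 4.1 the strata "will be included in the repeated measures linear mixed models models as stratification factors". Protocol 10.2.2 puts region and CM/EM in the models with no such limit.

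**The concern.** SAP 9.5.2 describes the mixed model with baseline values and strata and then, two sentences later, the logistic model with baseline values alone. A programmer following it would probably leave the strata out. One following protocol 10.2.2 would put them in. The same sensitivity analysis could therefore be run as two different models.

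The choice affects the estimate because an odds ratio is non-collapsible. When treatment has an effect and the strata predict response, a logistic model without them gives an odds ratio nearer 1 than the same model with them, even with complete data and perfect balance. Some precision for testing is lost too. The trial randomises within these strata, so the natural model includes them.

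Two related points of wording sit in the same text. The data window appears both as weeks 9 to 12 and as through week 12. The main CMH is described once on observed data and once after imputation.

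**Working it through.** The documents give no response rates or odds ratios for this endpoint, and the sample-size sections are redacted, so there is no plan figure to reproduce. Every response rate below is an assumption.

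**1. Hand calculation, region only.** Suppose baseline migraine days absorb CM/EM entirely and only region is lost. Assume placebo response of 25% and 40% in the two regions, a 60:40 split, and an odds ratio of 1.80 within each region.

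- Placebo odds: 0.25/0.75 = 0.333 and 0.40/0.60 = 0.667.
- Active odds: 1.80 × 0.333 = 0.600 and 1.80 × 0.667 = 1.200, so response is 0.375 and 0.5455.
- Pooled placebo: 0.6 × 0.25 + 0.4 × 0.40 = 0.310. Pooled active: 0.6 × 0.375 + 0.4 × 0.5455 = 0.4432.
- Odds ratio without region: (0.4432/0.5568) / (0.310/0.690) = 1.77, about 2% below 1.80.

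**2. Logistic model as written against the same model with strata.** Response follows logit(p) = constant + log(OR)·treatment + CM/EM term + region term + baseline term. Assumptions: 50:50 CM/EM and region; baseline days about 17 (SD 4.5) in CM and 8.5 (SD 2.7) in EM; 3/7 on active. Placebo response comes out at 36–48% in EM and 17–25% in CM. The columns at 1.8 are large-sample fits; those at 2.0 are simulations of 300,000 subjects.

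| Assumed OR for CM / region / 5 baseline days | At 1.8: as written, with strata | Lower by | At 2.0: as written, with strata | Lower by |
|---|---|---|---|---|
| 0.7 / 1.0 / 0.9 | 1.797, 1.800 | 0.2% | 1.987, 1.993 | 0.3% |
| 0.5 / 1.5 / 0.8 | 1.778, 1.800 | 1.2% | 1.963, 1.992 | 1.5% |
| 0.4 / 2.0 / 0.7 | 1.751, 1.800 | 2.7% | 1.929, 1.992 | 3.2% |
| 0.3 / 2.5 / 1.0 | 1.721, 1.800 | 4.4% | 1.886, 1.984 | 4.9% |

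The last row is an extreme: baseline days predict nothing beyond CM/EM, and region is a very strong predictor. At a true odds ratio of 1.0 the two models agree within simulation error.

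**3. Trial size.** 2,000 simulated comparisons were run with n = 234, about 134 on placebo and 100 on one dose, under the second and third scenarios.

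- Rejection at 0.05 with a true odds ratio of 1.0: 5.1% and 4.2% as written; 5.1% and 4.7% with strata.
- Power with a true odds ratio of 2.0: 67.8% and 62.9% as written; 68.9% and 64.8% with strata. The gain is 1.1 and 1.9 points.
- The standard error of the log odds ratio is about 0.29. The 2.7% shift is log(1.800/1.751) = 0.028, about a tenth of one standard error.

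**4. Comparison with the CMH.** The Mantel-Haenszel odds ratio over the four strata is Σ(a·d/n) / Σ(b·c/n). It conditions on strata but not on baseline days. Take a conditional odds ratio of 1.8 and let CM/EM act only through baseline days:

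- Log-odds slope −0.10 per day, region OR 1.25: CMH 1.776, logistic as written 1.800, with strata 1.803.
- Slope −0.15 per day, region OR 1.5: CMH 1.737, as written 1.779, with strata 1.788.

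In both, the model as written lies further from 1 than the CMH, and adding strata widens the gap (0.024 to 0.027; 0.042 to 0.051). With no baseline effect and region OR 2.0 the order reverses: as written 1.778, CMH 1.806.

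**The case against.** Most of the case against a stronger reading stands.

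- **Silence is not exclusion.** Protocol 10.2.2 can be read as bringing the strata in. SAP 4.1 requires them in the mixed models but does not forbid them elsewhere. Table 9-1 also omits covariates for the ANCOVA, yet SAP 9.5.1 names strata there. The code in Appendix B is redacted. This is an unsettled specification, not a proven omission.
- **The missing-data question is already covered.** A reader might infer that the plan lacks a check that changes only the missing-data rule. It has one: the stratified CMH after non-responder imputation in Table 9-1 sits beside the observed-data CMH with the same strata.
- **The strata do not explain the whole difference from the CMH.** A reader might infer that the logistic odds ratio must fall below the CMH odds ratio, or that adding strata would align the two. Step 4 shows that the order depends on how strongly baseline days predict response, and that the gap can widen.
- **Larger shifts describe another model.** Collapsing all four strata with no covariates takes 1.80 to 1.76 or 1.71 under assumed placebo rates of 20–45% or 15–50%. The planned model adjusts for baseline, so those figures do not apply to it.
- **The window wording is editorial.** SAP 2.1 fixes the endpoint at the last 4 weeks, and Table 5-1 defines the Week 12 interval.

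What remains is that the two documents support two different logistic models and that the one with strata is slightly better.

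**Conclusion.** This is a minor point. As written in SAP 9.5, SAP 9.5.2 and protocol 10.4.3.2, the logistic model adjusts for baseline values only, unlike the CMH and the mixed model for the same endpoint. Relative to the same model with strata, leaving them out lowers the odds ratio by about 0 to 3% at a true value of 1.8 (about 4% in the extreme scenario) and costs 1 to 2 points of power at 2.0. There is no shift under the null, so validity is not in question. The sizes rest on assumed response rates and baseline distributions; the direction, against the same model with strata, follows from non-collapsibility. It concerns one of several sensitivity analyses of a secondary endpoint reported with unadjusted p-values.

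The inconsistency over the main CMH deserves settling at the same time. If the text before Table 9-1 governs, the imputed CMH listed there as a sensitivity analysis repeats the main analysis, and the logistic model no longer changes the missing-data rule.

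**What to change.** Before unblinding, in SAP 9.5, 9.5.2 and Table 9-1:

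1. Specify the logistic model with treatment, baseline monthly migraine days, region and CM/EM. Use the strata as randomised, as SAP 9.1 already requires for efficacy analyses.
2. Refer throughout to the Week 12 monthly interval of Table 5-1 (the last 4 weeks).
3. State once whether the main CMH uses observed or non-responder-imputed data, bring SAP 9.5 and section 10 into line, and label the other version as the sensitivity analysis.
4. Extend SAP 4.1 beyond the mixed models so that it agrees with protocol 10.2.2.

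The cost is a few lines of SAP wording. Both factors are already recorded for randomisation, and no further data or subjects are needed.
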